## Protocol Summary

---

**Study Compound:** Atogepant

---

**Phase:** 3

---

**Study Objectives:**

To evaluate the safety and tolerability of atogepant 10 mg, atogepant 30 mg, and atogepant 60 mg for the prevention of migraine in participants with episodic migraine.

To prospectively test for superiority of atogepant 10 mg, atogepant 30 mg, and atogepant 60 mg versus placebo for the prevention of migraine in participants with episodic migraine.

---

**Study Design**

*Structure:* Multicenter, randomized, double-blind, placebo-controlled, parallel-group study.

*Duration:* The study will consist of a 4-week screening and baseline period, a 12-week double-blind treatment period, and a follow-up period of 4 additional weeks, for a total duration of 20 weeks.

*Study Intervention:* Atogepant 10 mg, atogepant 30 mg, and atogepant 60 mg tablets.

*Control:* Atogepant-matching placebo.

*Dosage/Dose Regimen:* Atogepant 10 mg, atogepant 30 mg, atogepant 60 mg, or placebo will each be administered once a day for 12 weeks duration.

*Randomization/Stratification:* Participants will be randomized to the following 4 arms in a 1:1:1:1 ratio:

- Placebo (n = 218)
- Atogepant 10 mg (n = 218)
- Atogepant 30 mg (n = 218)
- Atogepant 60 mg (n = 218)

Approximately 70% of randomized participants will have taken at least 1 prior migraine prevention medication, with proven efficacy (see Attachment 12.3). Randomization will be stratified based on prior exposure (yes/no) to a migraine prevention medication with proven efficacy (see Attachment 12.3).

*Visit Schedule:* Individual participant participation will begin with a 4-week screening/baseline period. Participants who complete the 4-week screening/baseline period and meet all entry criteria will be randomized at Visit 2 (Randomization Visit). The double-blind treatment period will last 12 weeks, with a follow-up period of 4 additional weeks.

There will be 8 scheduled clinic visits: Visit 1 (Screening/Baseline), Visit 2 (Randomization), Visit 3 (Week 2), Visit 4 (Week 4), Visit 5 (Week 6), Visit 6 (Week 8), Visit 7 (Week 12), and Visit 8 (Follow-up). The Visit 8 (Follow-up) must be completed for all participants who take at least one dose of study intervention, except for participants rolling over into Study 3101-309-002 (longterm safety extension study). For these participants Visit 8 is not required, as the Follow-up Visit will be performed in the longterm safety study. For participants who screen fail for the longterm safety, the Follow-up Visit must be completed. For details, please see Table 1 (Schedule of Visits and Procedures for In-Person Visits Conducted Prior to or During the COVID-19 Pandemic). To eliminate immediate potential hazards to participants and study staff due to the COVID-19 pandemic while ensuring participant safety and maintaining data integrity, the protocol was updated to allow

investigators/appropriately designated study staff to perform study visits remotely (as described in [Table 2](#) Schedule of Visits and Procedures for Visits Conducted Remotely Due to the COVID-19 Pandemic). If Visit 7 is conducted remotely, the participant will not be eligible to roll over into Study 3101-309-002; therefore, Visit 8 (Follow-up/End of Study) should be conducted as part of Study 3101-301-002. During the COVID-19 pandemic, Visit 8 (Follow-up/End of Study) should be conducted remotely for all participants in all cases.

### Study Population Characteristics

*Number of Participants/sites:* Approximately 872 participants will be randomized into the study from approximately 110 sites in the United States.

*Condition/Disease:* Migraine with aura or migraine without aura.

*Key Inclusion Criteria:*

- Male or female participants age 18 to 80 years, inclusive, at Visit 1.
- At least a 1-year history of migraine with or without aura consistent with a diagnosis according to [ICHD-3, 2018](#).
- Age of the participant at the time of migraine onset < 50 years.

*Key Exclusion Criteria:*

- Has a history of migraine accompanied by diplopia or decreased level of consciousness or retinal migraine as defined by ICHD-3, 2018.
- Has a current diagnosis of chronic migraine, new persistent daily headache, trigeminal autonomic cephalgia (eg, cluster headache), or painful cranial neuropathy as defined by ICHD-3, 2018.

- History of an inadequate response to > 4 medications (2 of which have different mechanisms of action) prescribed for the prevention of migraine (see [Attachment 12.3](#) for classification of inadequate response to migraine-preventive medications).

- Participants with clinically significant hematologic, endocrine, cardiovascular, pulmonary, renal, hepatic, gastrointestinal, or neurologic disease.

---

### Response Measures

*Efficacy:* Migraine days; headache days; acute medication use days.

*Health Outcomes:* Activity Impairment in Migraine – Diary (AIM-D);

Migraine-Specific Quality of Life Questionnaire, version 2.1 (MSQ v2.1);

Activity Level and Activity Limitation; and Patient-Reported Outcomes Measurement Information System Pain Interference – Short Form 6a (PROMIS-PI).

*Pharmacokinetics:* Pharmacokinetic samples will be collected for analysis for participants who consent.

*Safety:* Adverse events, physical examinations, clinical laboratory determinations, vital sign measurements, electrocardiogram (ECG) parameters, and the Columbia-Suicide Severity Rating Scale (C-SSRS).

#### **General Statistical Methods and Types of Analyses:**

All efficacy analyses will be performed using the modified intent-to-treat (mITT) population which consists of all randomized participants who received at least 1 dose of study intervention, had an evaluable baseline period of eDiary data and at least 1 evaluable postbaseline 4-week period (Weeks 1 to 4, 5 to 8, and 9 to 12) of eDiary data during the double-blind treatment period. All safety analyses will be performed using the safety population which consists of all participants who took at least 1 dose of study intervention. The analysis population for Off-treatment Hypothetical Estimand includes all randomized participants who received at least 1 dose of study treatment, had an evaluable baseline period of eDiary data and had at least 1 evaluable post-baseline 4-week period (Weeks 1 to 4, 5 to 8, 9 to 12) of eDiary data during the double-blind treatment period and follow-up period, regardless of whether on study treatment or off study treatment.

The primary efficacy endpoint is the change from baseline in mean monthly migraine days across the 12-week treatment period.

The primary comparison between treatment groups will be done by a mixed-effects model for repeated measures (MMRM) of the change from baseline. The statistical model will include treatment group, visit, prior exposure (yes/no) to a migraine prevention medication with proven efficacy, and treatment group by visit interaction as categorical fixed effects. It will also include the baseline score and baseline-by-visit interaction as covariates. An unstructured covariance matrix will be used to model the covariance of within-participant repeated measurements. The Kenward-Roger approximation (Kenward 1997) will be used to estimate the denominator degrees of freedom. The analysis will be performed based on all postbaseline values using only the observed cases without imputation of missing values. Pairwise contrasts in the MMRM model will be used to make the pairwise comparisons of each atogepant dose to placebo.

Secondary efficacy endpoints for the United States and the European Union:

- Change from baseline in mean monthly headache days across the 12-week treatment period.
- Change from baseline in mean monthly acute medication use days across the 12-week treatment period.
- $\geq 50\%$  reduction in 3-month average of monthly migraine days.
- Change from baseline in MSQ v2.1 Role Function-Restrictive domain score at Week 12
- Change from baseline in mean monthly Performance of Daily Activities domain score of the AIM-D across the 12-week treatment period.
- Change from baseline in mean monthly Physical Impairment domain score of the AIM-D across the 12-week treatment period.

[figure not shown]
The secondary endpoints for headache days, acute medication use days, MSQ v2.1 Role Function-Restrictive domain score, Performance of Daily Activities domain score of the AIM-D, and Physical Impairment domain score of the AIM-D will be analyzed in the same manner as that used to analyze the primary endpoint.

The secondary endpoint of 50% responders, defined as participants with at least a 50% reduction from baseline in the 3-month average of monthly migraine days, will be assessed for each individual. A logistic regression model will be used to analyze the 50% responders across the 12-week treatment period. This model assumes a binary distribution for the response and uses a logit link. The analysis model will include treatment group, prior exposure (yes/no) to a migraine prevention medication with proven efficacy, and baseline monthly migraine days. The treatment difference in terms of odds ratio between each atogepant dose group and placebo will be estimated and tested from this model.

Incidence of treatment-emergent adverse events (TEAEs) will be tabulated by primary system organ class (SOC) and by specific event within each primary SOC. Treatment-emergent adverse events will be analyzed after treatment start on Day 1 through the end of the study.

[figure not shown]
*Sample Size Calculation:* A sample size of 218 randomized participants per treatment group will provide at least 98% power to detect the treatment difference between each of the 3 atogepant doses (assumed equally effective) and placebo for the primary efficacy endpoint. This sample size was selected to provide sufficient power for each of the primary and first 3 secondary endpoints. The power calculations are based on the following assumptions: 1) the standard deviation and treatment difference from placebo will be similar to the average value across the migraine prevention studies for atogepant (Phase 2/3 Study CGP-MD-01), telcagepant (Ho 2014) and monoclonal antibodies (Dodick 2014a; Dodick 2014b; Bigal 2015). In particular, the assumed treatment difference from placebo in change from baseline in mean monthly migraine days across the 12-week treatment period is -1.5 days, and the standard deviation is 3.5 days; and 2) the study statistical testing plan controls the overall type I error at 5%. The power calculations of the primary and secondary endpoints have taken the multiple comparisons into consideration by testing each dose versus placebo at a 0.0167 significance level, 2-sided.

**Figure 1 Study Diagram**

[figure not shown]

[figure not shown]
**Table 1 Schedule of Visits and Procedures for In-Person Visits Conducted Prior to or During the COVID-19 Pandemic**

[figure not shown]
Approval Date: 15-May-2020 16:33:54 (GMT)

[figure not shown]

Approval Date: 15-May-2020 16:33:54 (GMT)

Approval Date: 15-May-2020 16:33:54 (GMT)

Approval Date: 15-May-2020 16:33:54 (GMT)

## 1. Background and Clinical Rationale

### 1.1 Background

Migraine affects 18% of women and 6% of men in the United States with peak prevalence occurring between the ages of 25 to 55 years. Approximately one-third of patients with migraines have 3 or more migraine headaches per month, and over half report severe impairment or the need for bed rest (Lipton 2007). In the United States alone, work loss due to migraine is estimated to cost ~ \$13 billion annually (Hu 1999). Prevalence is similar in Europe, with migraine headache affecting on average 17.6% of women and 8% of men (Stovner 2010). The Global Burden of Disease Survey 2010 (GBD2010) estimated the global prevalence of migraine to be 14.7%, making it the third most common disease in the world in both males and females. Migraine was ranked seventh highest among specific causes of disability globally (Steiner 2013).

Migraine is typically characterized by attacks of throbbing, unilateral headache of moderate or severe pain intensity, associated with nausea, vomiting, and/or sensitivity to light (photophobia), and sound (phonophobia). In about 25% of individuals, the migraine headache is preceded by focal neurological dysfunction (aura). Improving diagnosis and optimizing treatments for migraine have been recognized as critically important to overcoming current barriers to reduce the global burden of migraine.

Because there are no biological markers for migraine, diagnosis is based on clinical history, examination, and the exclusion of other headache disorders. Physicians apply clinical criteria to guide diagnoses and subsequent treatment. Episodic migraine is a syndrome diagnosis applied to patients with migraine (with or without aura) who have 1 to 14 headache days per month. Chronic migraine is a specific ICHD-3 diagnosis applied to a subset of patients with  $\geq 15$  headache days per month (Katsarava 2012; Olesen 2004; ICHD-3, 2018). This study will evaluate the efficacy, safety and tolerability of atogepant in participants with EM.

### 1.2 Overview of Atogepant

Atogepant is a potent, selective oral CGRP receptor antagonist being developed for migraine prevention. CGRP is a neuropeptide implicated in the pathophysiology of migraine. CGRP levels in the cranial venous outflow (ie, external jugular vein) are increased during a migraine attack and exogenously administered CGRP has been shown to trigger migraine-like headache in people with migraine. The majority (80 to 90%) of trigeminal A $\delta$  fibers that innervate the dura contain CGRP, suggesting that these fibers may be involved in sterile neurogenic inflammation and migraine pain transmission. Furthermore, the CGRP

receptor is present on human meningeal and cerebral blood vessels. These observations suggest that activation of the trigeminovascular system, with release of CGRP, may play a key role in migraine pathogenesis and that inhibition of CGRP may yield a novel therapeutic approach to treating migraine.

The ability of CGRP inhibition to induce pain relief in the acute treatment of migraine was initially observed with an IV formulation of olcegepant (Olesen 2004), and replicated by Merck & Co., Inc with an oral formulation of MK-0974 (telcagepant), a highly selective CGRP receptor antagonist. In Phase 3 studies, telcagepant was superior to placebo in the primary endpoints of 2-hour pain freedom, 2-hour pain relief, and the absence of associated symptoms (photophobia, phonophobia, and nausea), as well as the key secondary endpoint of 24-hour sustained pain freedom (Connor 2009). However, serum ALT increases were observed with telcagepant. For this reason, the development of these oral CGRP receptor antagonists was stopped.

A Phase 2/3 clinical study (Study CGP-MD-01) was conducted, which compared atogepant 10 mg once a day, atogepant 30 mg once a day, atogepant 30 mg BID, atogepant 60 mg once a day and atogepant 60 mg BID to placebo in EM prevention. Overall, all the atogepant doses tested were well tolerated and the AE profile of all atogepant doses did not significantly differ from placebo. For the primary efficacy endpoint of change from baseline in mean monthly migraine days across the 12-week treatment period, all atogepant doses demonstrated a statistically significant reduction compared to placebo in patients with EM.

Additional information on non-clinical pharmacology, toxicology, and PK properties of atogepant can be found in the IB.

### 1.3 Study Rationale

Based on the results of the Phase 2/3 Study CGP-MD-01, the present study is being performed to prospectively assess the safety, tolerability and efficacy of atogepant 10 mg, atogepant 30 mg, and atogepant 60 mg compared with placebo in the prevention of EM. This randomized, double-blind, placebo-controlled Phase 3 study is designed to be a pivotal trial to confirm the efficacy of these doses and dose regimens and will be used to support registration applications.

[REDACTED]

## 2. Study Objectives and Clinical Hypotheses

### 2.1 Study Objectives

- To evaluate the safety and tolerability of atogepant 10 mg, atogepant 30 mg, and atogepant 60 mg for the prevention of migraine in participants with EM.
- To prospectively test for superiority of atogepant 10 mg, atogepant 30 mg, and atogepant 60 mg versus placebo for the prevention of migraine in participants with EM.

## 3. Study Design

This is a multicenter, randomized, double-blind, placebo-controlled, parallel-group study conducted at approximately 110 sites in the United States.

Approximately 872 participants will be randomized to one of 4 treatment arms (placebo, atogepant 10 mg, atogepant 30 mg, and atogepant 60 mg) in a 1:1:1:1 ratio as follows:

- Placebo (n = 218)
- Atogepant 10 mg (n = 218)
- Atogepant 30 mg (n = 218)
- Atogepant 60 mg (n = 218)

Approximately 70% of randomized participants will have taken at least 1 prior migraine prevention medication with proven efficacy (see Attachment 12.3). Randomization will be stratified based on prior exposure (yes/no) to a migraine prevention medication with proven efficacy (see Attachment 12.3).

Participant participation will begin with a 4-week screening/baseline period. Participants who complete the 4-week screening/baseline period and meet all entry criteria will be randomized to the double-blind treatment period of the study at Visit 2 (Randomization Visit). The double-blind treatment period will last 12 weeks, with a subsequent follow-up period of 4 additional weeks. There will be 8 scheduled clinic visits: Visit 1 (Screening/Baseline), Visit 2 (Randomization), Visit 3 (Week 2), Visit 4 (Week 4), Visit 5 (Week 6), Visit 6 (Week 8), Visit 7/ET (Week 12), and Visit 8 (Follow-up). For details, please see Table 1 (Schedule of Visit and Procedures for In-Person Visits Conducted Prior to or During the COVID-19 Pandemic). To eliminate immediate potential hazards to participants and study staff due to the COVID-19 pandemic while ensuring participant safety and maintaining data integrity, the protocol was updated to allow investigators/appropriately designated study staff to perform study visits remotely (as described in Table 2 Schedule of Visits and Procedures for Visits Conducted Remotely Due to the COVID-19 Pandemic).

Participants completing the double-blind treatment period in this study may be eligible to continue in Study 3101-309-002, a longterm extension safety study in participants with EM, if they are at a participating site. For these rollover participants, a Visit 8 is not required in the present study, as the Follow-up Visit will be performed in the longterm safety study. For participants who screen fail for the longterm safety study, the Follow-up Visit must be completed. If Visit 7 is conducted remotely due to the COVID-19 pandemic, the participant will not be eligible to roll over into Study 3101-309-002; therefore, Visit 8 (Follow-up/End of Study) should be conducted remotely as part of Study 3101-301-002.

### **3.1 Data Safety Monitoring Board**

An independent DSMB will be established to review unblinded safety data and summary reports, identify any safety issues and trends, and make recommendations to Allergan, including modification or early termination of the trial, if emerging data show unexpected and clinically significant AEs of treatment.

Details of the DSMB memberships, standard operational procedures for data monitoring/review, frequency of review, and other pertinent details will be provided in a separate DSMB Charter.

### 3.2 Adjudication Committee

An Adjudication Charter will be established and will describe the process for the blinded surveillance, monitoring, and adjudication by the Clinical Adjudication Committee of events of post-treatment elevations of ALT and/or AST  $\geq 3 \times$  the ULN in the atogepant program. The purpose of this committee charter will be to provide a standardized process for the adjudication of data associated with these events in order to determine whether the elevation was related to atogepant.

## 4. Study Population and Entry Criteria

### 4.1 Number of Participants

Approximately 872 participants will be randomized at approximately 110 sites in the United States.

### 4.2 Inclusion Criteria

The following are requirements for entry into the study:

1. Written informed consent and participant privacy information (eg, written authorization for use and release of health and research study information) obtained from the participant prior to initiation of any study-specific procedures.
2. Male or female participants ages 18 to 80 years, inclusive, at Visit 1.
3. At least a 1-year history of migraine with or without aura consistent with a diagnosis according to the [ICHD-3, 2018](#).
4. Age of the participant at the time of migraine onset  $< 50$  years.

### 4.3 Exclusion Criteria

The following are criteria for exclusion from participating in the study:

[figure not shown]
- [REDACTED]
2. Has a history of migraine accompanied by diplopia or decreased level of consciousness or retinal migraine as defined by ICHD-3, 2018.
  3. Has a current diagnosis of chronic migraine, new persistent daily headache, trigeminal autonomic cephalgia (eg, cluster headache), or painful cranial neuropathy as defined by ICHD-3, 2018.

[figure not shown]
- [REDACTED]
6. History of an inadequate response to > 4 medications (2 of which have different mechanisms of action) prescribed for the prevention of migraine (see Attachment 12.3 for classification of inadequate response to migraine-preventive medications).

- [REDACTED]
12. Clinically significant cardiovascular or cerebrovascular disease [REDACTED]

15. Any clinically significant hematologic, endocrine, pulmonary, renal, hepatic, gastrointestinal, or neurologic disease:

[figure not shown]

Approval Date: 15-May-2020 16:33:54 (GMT)

#### 4.4 Permissible and Prohibited Medications/Treatments

[figure not shown]
##### 4.4.1 Permissible Medications/Treatments

[figure not shown]
Medications that are not specifically prohibited in Section 4.4.2 are allowed, with the following clarifications and restrictions:

Therapy considered necessary for the participant's welfare may be given at the discretion of the investigator. [REDACTED]

##### 4.4.2 Prohibited Medications/Treatments

The decision to administer a prohibited medication/treatment is done with the safety of the study participant as the primary consideration. When possible, Allergan should be notified before the prohibited medication/treatment is administered.

#### **4.4.3 Definition of Women of (Non-)Childbearing Potential and/or Acceptable Contraceptive Methods**

For the purposes of this study, women will be considered of childbearing potential unless they are naturally postmenopausal (ie, no menses for 2 years) or permanently sterilized (ie, bilateral tubal ligation, bilateral tubal occlusion [eg, Essure® placement with HSG confirmation], bilateral salpingectomy, bilateral oophorectomy, or hysterectomy). For women

of childbearing potential who may participate in the study, the following methods of contraception, if properly used, are generally considered highly effective:

- Combined (estrogen and progestogen containing) hormonal contraception such as oral, intravaginal, or transdermal (ie, pill, patch, vaginal ring)
- Progestogen-only hormonal contraception (with inhibition of ovulation) that are oral, injectable, or implantable
- IUD or IUS
- Vasectomized partner (provided that the partner is the sole sexual partner of study participant and that the vasectomized partner has received medical assessment of the surgical success)
- Sexual abstinence (defined as refraining from heterosexual intercourse for the duration of the study)

Acceptable birth control methods which may not be considered as highly effective:

- Progestogen-only oral hormonal contraception (where inhibition of ovulation is not the primary mode of action)
- Male or women condom with or without spermicide (women and male condoms should not be used together)
- Cap, diaphragm or sponge with spermicide
- A combination of male condom with either cap, diaphragm or sponge with spermicide (double-barrier methods) are also considered acceptable, but not highly effective, birth control methods.

For males who may participate in the study, the following methods of contraception, if properly used, are generally considered reliable: post-bilateral vasectomy, barrier contraception or sexual abstinence. Male participants must also refrain from donating sperm during the course of the study.

The investigator and each participant will determine the appropriate method of contraception for the participant during the participation in the study.

If a woman becomes pregnant during the study, the investigator will notify Allergan immediately after the pregnancy is confirmed and the participant will be exited from the study after appropriate follow-up. The investigator will (1) notify the participant's physician that the participant was being treated with an investigational drug atogepant and (2) follow the progress of the pregnancy. The investigator must document the outcome of the pregnancy and provide a copy of the documentation to Allergan.

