### 5.3 Methods for Masking/Blinding

A double-dummy design will be used to maintain study blind. Atogepant tablets and matching placebo will be provided in identical blister cards to maintain masking of the study.

All participants will be instructed to take study intervention once a day (3 tablets) at approximately the same time each day. Participants will therefore, receive either placebo, atogepant 10 mg, atogepant 30 mg, or atogepant 60 mg once a day.

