### 5.4 Intervention Allocation Ratio

Participants will be randomized to the following 4 arms in a 1:1:1:1 ratio:

- Placebo (n = 218)
- Atogepant 10 mg (n = 218)
- Atogepant 30 mg (n = 218)
- Atogepant 60 mg (n = 218)

Approximately 70% of randomized participants will have taken at least 1 prior migraine prevention medication with proven efficacy (see Attachment 12.3). Randomization will be stratified based on prior exposure (yes/no) to a migraine prevention medication with proven efficacy (see Attachment 12.3).

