**Table 5-1 Study Interventions**

Drug/Dose	Study Intervention Product	Study Intervention Frequency	Route of Administration
Placebo	Placebo 10 mg/ Placebo 30 mg/ Placebo 60 mg	Once daily	Oral
Atogepant 10 mg	Atogepant 10 mg/Placebo 30 mg/ Placebo 60 mg	Once daily	Oral
Atogepant 30 mg	Atogepant 30 mg/Placebo 10 mg/ Placebo 60 mg	Once daily	Oral
Atogepant 60 mg	Atogepant 60 mg/Placebo 10 mg/ Placebo 30 mg	Once daily	Oral

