### 7.3 Hypothesis and Methods of Analysis

For efficacy analyses, data will be analyzed according to participants' randomization assignments, regardless of actual treatment received.

For safety data analyses, the participants will be analyzed according to actual treatment received (rather than as randomized).

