#### 9.4 Exposure to Study Intervention During Pregnancy

Details of all pregnancies in female participants and female partners of male participants will be collected after the start of study intervention and until the Follow-up Visit (Visit 8) or 30 days after the last dose of study intervention if the Follow-up Visit is not done. Study center personnel must report every pregnancy on the pregnancy form within 24 hours of learning of the pregnancy to the **SAE/pregnancy fax number**, [REDACTED] even if no AE has occurred. The pregnancy must be followed to term and the outcome reported by completing a follow-up pregnancy form. Abnormal pregnancy outcomes (eg, spontaneous abortion, fetal death, stillbirth, congenital anomalies, ectopic pregnancy) are considered SAEs. Elective abortions can be SAEs or AEs depending on the reason for the elective abortion (eg, fetal death, still birth, congenital anomalies, ectopic pregnancy, which would make the elective abortion an SAE). For pregnancy-related SAEs, in addition to the pregnancy form, a separate SAE form must be filed as described in Section 9.3 with the appropriate serious criterion (eg, hospitalization) indicated.

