### 9.6 Procedures for Unmasking of Study Intervention

The IWRS will be programmed with blind-breaking instructions. In case of an emergency, the investigator has the sole responsibility for determining if unblinding of a participant's study intervention assignment is warranted. Participant safety must always be the first consideration in making such a determination. If the investigator decides that unblinding is warranted, the investigator should make every effort to contact the Allergan Medical Monitor

prior to unblinding a participant's study intervention assignment unless this could delay emergency treatment of the participant. If a participant's study intervention assignment is unblinded, the Allergan Medical Monitor must be notified within 24 hours after breaking the blind. The date and reason that the blind was broken must be recorded in the source documentation.

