18.1 Efficacy Evaluation

Efficacy Endpoints

Table 18–1 describes the collection devices for primary and key secondary endpoints. The primary endpoint and 5 key secondary endpoints are collected via eDiary according to protocol design. Minimal disruption is expected for these endpoints because participants are expected to complete eDiary at home and submit the responses every day.

The endpoint, MSQ v2.1 Role Function Restrictive domain score at Week 12, will be collected using eTablet as one electronic patient reported outcome (ePRO) at site. The remote collection for this endpoint was in production starting from April 20,2020. Participants are required to complete the ePRO measures remotely at Visit 7 (Week 12) according to remote-visit procedure (Table 4–2).

To evaluate the missing rate for this endpoint at Week 12, the number of participants who missed at least one ePRO assessment due to COVID-19 will be summarized at each visit in the mITT Population (efficacy analyses population).

Table 18–1 Summary of Collection Devices for Primary and Key secondary endpoints

Hypothesis Testing	Node	Endpoint	Collection device
Primary	P1	Change from baseline in mean monthly migraine days across the 12-week treatment period	eDiary
Secondary 1	S1	Change from baseline in mean monthly headache days across the 12-week treatment period	eDiary
Secondary 2	S2	Change from baseline in mean monthly acute medication use days across the 12-week treatment period	eDiary
Secondary 3	S3	≥ 50% reduction in 3-month average of monthly migraine days	eDiary
Secondary 4	S4	Change from baseline in MSQ v2.1 Role Function Restrictive domain score at Week 12	eTablet
Secondary 5	S5	Change from baseline in mean monthly Performance of Daily Activities domain score of the AIM-D across the 12-week treatment period.	eDiary
Secondary 6	S6	Change from baseline in mean monthly Physical Impairment domain score of the AIM -D across the 12-week treatment period.	eDiary

Power and Sample Size Evaluation

The study achieved the last participants first visit on January 31, 2020. A total of 910 patients were randomized, and the number of randomized participants exceeded the planned sample size 872. It is expected the missing rate during the pandemic might be slightly higher than the missing rate before the pandemic. No big impact for the power and sample size calculation is anticipated.

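### Section 4.4.3 has the investigator tell a pregnant participant's physician that she was being treated with atogepant, which is untrue in the placebo arm and unknowable under the blind

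*Protocol*

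**What the plan says.** Protocol Section 4.4.3 ends with what happens if a woman becomes pregnant during the study. The investigator informs the sponsor, and then has two further duties. One is to follow the pregnancy. The other is to "notify the participant's physician that the participant was being treated with an investigational drug atogepant". The duty applies to every pregnant participant, whatever her arm, and mentions neither placebo nor the blind.

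The design sections describe the treatment differently:

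- Section 5.3: "A double-dummy design will be used to maintain study blind". Every participant takes three tablets a day from identical blister cards.
- Section 5.4: "Participants will be randomized to the following 4 arms in a 1:1:1:1 ratio", with 218 planned in each arm.
- Table 5-1 gives the placebo regimen as "Placebo 10 mg/ Placebo 30 mg/ Placebo 60 mg", so that arm takes no atogepant.

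Two other sections bear on the same event. Section 9.4 deals with reporting to the sponsor: "Study center personnel must report every pregnancy on the pregnancy form within 24 hours of learning of the pregnancy". It speaks of study intervention rather than of atogepant. Section 9.6 deals with breaking the blind: "In case of an emergency, the investigator has the sole responsibility for determining if unblinding of a participant's study intervention assignment is warranted".

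**The concern.** The instruction presents exposure to the active drug as established fact. In a blinded, placebo-controlled trial it is not established at the time the notice is due. For a woman on placebo the statement is wrong. For a woman on any dose it happens to be right, but the investigator has no basis for it while the blind holds.

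The recipient is an outside physician managing a pregnancy. The protocol does not require that physician to be told that the study was blinded, that there was a placebo arm, or that the assignment can be obtained if care depends on it. A definite statement of investigational-drug exposure in pregnancy may then enter the medical record of someone who never took the drug. What is at stake is the accuracy of one safety communication, not the trial's inference.

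**Working it through.** **Inputs.** Allocation 1:1:1:1 and 218 per arm (Protocol 5.4); about 872 randomized in total (Protocol 4.1); placebo regimen (Table 5-1); 910 actually randomized (SAP 18.1).

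**The plan's arm sizes.** 4 × 218 = 872, which agrees with the stated total.

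**Share for whom the statement is false.** Placebo share = 218/872 = 0.250, or 25.0%. The remaining 3 × 218/872 = 75.0% are assigned to atogepant.

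**Share after enrolment.** The SAP reports "A total of 910 patients were randomized, and the number of randomized participants exceeded the planned sample size 872". Equal allocation gives 910/4 = 227.5 per arm. Since 227/910 = 24.95% and 228/910 = 25.05%, the expected share is still about 25%. Actual counts by arm are not given.

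**From randomized participants to notices.** If pregnancy is equally likely in every arm, about one notice in four is expected to be false. The documents give neither pregnancy rates by arm nor an expected number of pregnancies, so the calculation stops at a proportion.

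**Can the investigator know the assignment?** Kits are dispensed by number through the IWRS (Protocol 5.5). Treatment codes for the pharmacokinetic samples stay within the bioanalytical team (Protocol 6.3). The route to an individual assignment during the study is the emergency provision in Section 9.6. That section does not mention pregnancy, and Section 4.4.3 does not ask for the blind to be broken before the physician is told.

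**Does another section put it right?**

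| Section | What it covers | Does it qualify the notice? |
|---|---|---|
| 4.4.3 | Notice to the participant's physician | No; asserts atogepant treatment |
| 9.4 | Pregnancy report to the sponsor, follow-up to term | No; its terms suit a blinded trial, but it does not say what the physician is told |
| 9.6 | Emergency unblinding | No; pregnancy neither listed nor excluded |

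**Does the error reach the analysis?** No. Pregnancies come to the sponsor on their own forms under Section 9.4. Assignment is held in the IWRS. Section 7.3 states: "For safety data analyses, the participants will be analyzed according to actual treatment received", and SAP Section 6 says the same of the Safety Population. What the physician was told is not an input to any analysis.

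**The case against.** The strongest reply is that this is loose wording rather than a fault in the design. Section 4.4.3 states what the notice should convey; it is not a script, and nothing stops an investigator from adding that the study is blinded and placebo-controlled. Presuming exposure is also the cautious direction in pregnancy, and Section 9.6 lets the investigator unblind when safety requires it. Consent pages are not available here, nor are the pregnancy form and the Study Reference Manual, and these may govern what is actually said.

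The 25% can be questioned too. Its base is all randomized participants, including men and postmenopausal women, and it is not a share of pregnancies.

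Timing limits the practical gain. The last participant's first visit was 31 January 2020, and this protocol version carries an approval date of 15 May 2020. Allowing 35 days of screening, 84 of treatment and 28 of follow-up, and ignoring visit slippage, the last participant would finish dosing about 29 May and follow-up about 26 June 2020. A rewording at this version would have reached few people.

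Much of this stands, and it fixes the weight of the point as low. It does not make the sentence right. Caution is served equally well by saying she may have received atogepant, and that wording also tells the physician that the assignment is uncertain. The option to unblind does not help, because the notice is required whether or not the blind is broken. That a site might add the missing context on its own initiative is no defence of an instruction that omits it.

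**Conclusion.** The point holds. Section 4.4.3 contains an operative, unconditional instruction to state something that is false for the placebo arm, planned at 25.0% of randomized participants, and that a blinded investigator cannot verify for any participant. No other section in the available text qualifies it.

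The reading of about one false notice in four rests on equal pregnancy rates across arms. That physicians' records would in fact be wrong is a possibility that follows from the wording, not something the documents show. The impact is low: it is a small matter of accurate safety information for an individual participant's care, and a change that could be made rather than one that must be.

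**What to change.** Reword item (1) of the pregnancy paragraph in Section 4.4.3 along these lines: the investigator will inform the participant's physician that she took part in a double-blind study and may have received atogepant (10, 30 or 60 mg) or placebo; the actual assignment will be given if the blind is broken under Section 9.6, or after the study is unblinded.

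The cost is one protocol sentence, with no change to procedures, data collection or analysis. The physician receives a less definite statement while the blind is held, which reflects what the investigator knows. If the trial is too far advanced for an amendment to be useful, the correction still belongs in the sponsor's template for later blinded studies.
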